The Study Guide Trial 2017: The Study Guide Cluster Randomized Control Trial

NCT03312218

MARCH 2017

Each year, over 1,200 residents challenge the Family Medicine certification exam. Scores obtained by candidates on national licensing exams are positively associated with the quality of patient care provided in future practice.¹⁻⁵ Therefore, educational methods to optimize residency training are vitally important.

This research is needed to improve residency training. Our objective is to deliver a trial-validated mobile application as a tool for improving the knowledge of future physicians. Through this definitive trial, we can advance residency training for thousands of physicians, for years to come.

Background

As a guide for residents preparing for their certification exam, the College of Family Physicians of Canada (CFPC) elaborated the concept of Priority Topics.⁶ A major challenge for residents is knowledge retention.^{7,8} To address this challenge, the strategy of spaced education emerged from research in educational psychology.⁹ Spaced education takes advantage of (1) the spacing effect and (2) the testing effect.^{10,11} With the *spacing effect*, students can increase their retention of information by interval rereading of content. The *testing effect* refers to the following: when combined with answer feedback, the process of testing one's knowledge alters learning itself, to improve recall.¹²⁻¹⁵ Greater resident engagement in self-learning is needed to implement spaced education. In this context, it is critical to test interventions to enhance such engagement. Building on the findings of our prior CIHR-funded research and a pilot study, this proposal is grounded in a 'qualitative knowing' of the context of residency training in Family Medicine.¹⁶

Literature: Randomized controlled trials demonstrate that spaced education can boost long-term knowledge retention among students and residents in Urology.¹⁷⁻²¹ Outside of Urology, we found four small single-site trials of spaced education in residency (General Surgery, Oncology, Internal Medicine and Pediatrics).²²⁻²⁵ We found no published studies of spaced education in the context of Family Medicine. Guided by a specialized librarian, our searches were conducted iteratively in Google Scholar and three databases - PubMed, EMBASE, and ERIC. We provide our search strategies, and a summary of findings table, in the appendix.

Importance

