What are the proposed arrangements for allocating participants to trial groups? One co-applicant (JK) will conduct a computer generated and blinded central randomization procedure of universities (clusters) to trial groups. As the unit of randomization, all Canadian universities will be stratified per the median number of residents by site, and then randomly allocated to the intervention or the control arm. This will minimize the effect of any inequality between clusters on the results. Following randomization, recruitment will begin locally as co-investigators at each site will obtain a list of their eligible residents. Consenting residents will then receive a coupon to install the app by the start date. The period from July to November 2017 will provide ample time to obtain consent. Participants will exit the study on the first day of their exam in the spring of 2019.

What are the proposed methods for protecting against sources of bias? Trial outcomes (exam scores and questions completed) are objectively assessed. Residents will be blinded to the nature of the intervention. Our consent form will not mention our research questions or the intervention. The certification exam will be scored by persons unaware of group allocation.

How will contamination be addressed? Participants will unlock the trial versions of the app using a coupon with a unique login number. We will track logins for each unique ID. With this tracking, intervention group residents will not access the version of the app destined for control group residents, or vice versa. In addition, randomization at geographically dispersed sites will limit the ability of intervention group residents to influence those allocated to the control group. Residents at different universities share no core rotations.

What are the planned inclusion/exclusion criteria? All incoming family medicine residents in Canada will be eligible. These eligible residents will be clustered within university training programs. We will exclude residents from other specialties who happen to be on rotation in Family Medicine. We will deliver the intervention from December 2017 to April 2019 (70 weeks). We will follow each resident and provide tech support.

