What are the proposed primary and secondary outcome measures? Our primary outcome will be the score on the written component of the CFPC certification exam in April 2019. Co-applicant CB is authorized by the CFPC to provide de-identified scores for each participant. We will also test the hypothesis that alerts to reinforcement of content result in greater resident engagement with test questions, as compared with control residents not exposed to alerts to reinforcement of content. Therefore, our secondary outcome will be the number, percentage and time to completion of all correctly answered questions, per case. These data will help explain the expected improvement in exam scores.

Using a study “dashboard”, we will monitor app usage over time at the group level, by examining a dynamic count of answered questions. In addition to counting attempts and correctly answered questions, the date and time of each attempt will be tracked and automatically recorded at the server. Thus, for each

case and for each participant, we will calculate a time to completion of that case. This will be defined by counting the number of days from the study start date in 2017 to the date that test questions for that case were deemed to be correctly answered.

Through a baseline questionnaire, we will collect data on potential confounders at the participant level: age, sex, Canadian or International Medical Graduate status and whether they hold a graduate degree.

What is the proposed sample size and what is the justification for the assumptions underlying the power calculations? We will have 80% power to detect an effect size of 0.4 (Cohen's d). This effect corresponds to a 4% absolute increase in score, equivalent to two additional correct exam questions. Assumptions: Clusters will provide an average of 80 residents. Given this projected number, we will consent a minimum of $8 \times 80 = 640$ residents at 8 university training sites. If residents at 12 sites are consented, we will have adequate power to detect an effect size of 0.4. These assumptions are based on pilot study findings as well as actual scores obtained by all residents in Canada on the certification exams conducted in the spring of 2015 and the spring of 2016. We detail our calculation of the proposed sample size (and the design effect) in the appendix.

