What is the planned recruitment rate? What evidence is there that the planned recruitment rate is achievable? With support from co-investigators and collaborators, each university will recruit at least 80% of their residents. The evidence for this comes from our pilot study, in which we consented more than 80% of residents at two university sites in Quebec and Ontario. This is not surprising; residents perceive a need for an app based on Priority Topics to help pass a high-stakes exam. We will report the number of residents eligible for participation in both study arms, their flow through the study and losses to follow up using a CONSORT-style flow diagram. While we anticipate a small loss of consenting residents to follow up, for example at McGill just two residents transfer out, on average per year.

What is the proposed type of analyses? We will follow the guidelines of the CONSORT statement for clustered randomized trials and recommendations for their analysis when presenting and analysing our data.²⁹ The primary efficacy analysis will be based on the intention-to-treat population i.e. all study participants will be analysed as randomized. The primary statistical analysis will evaluate the difference in mean exam scores between residents in the intervention and control groups using a linear mixed effects model. The mixed model will incorporate study site as a random factor and the following fixed factors (as presumed predictors of exam score): study group assignment (control / intervention), age, sex, completion of a graduate degree, and IMG status. The estimated fixed effects will be reported along with 95% confidence intervals. Confirmatory assessment of the primary endpoint will be based on the confidence interval for the fixed effect estimate of "study group", implying a two-sided level of significance (against the null hypothesis of no effect) of 0.05.

Regarding the secondary outcome of time to correct completion of test questions: For each resident, a mean time to event (with confidence intervals) will be calculated separately for each clinical case in the app, averaged and then compared across groups. These data will be described using a Kaplan-Meier curve. To account for clustering while adjusting for potential confounders, we will use a Cox regression model with a sandwich covariance structure. In the adjusted model, we will compare the hazard for this secondary outcome, between intervention and control groups, as of April 2019.

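### Does the unconditional 80% power claim contradict the 8-site minimum, given that the plan also ties adequate power to 12 sites?

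*Combined protocol and SAP*

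**What the plan says.** The sample size section of the combined protocol and SAP makes three statements in one paragraph.

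- Power, with no site count attached: "We will have 80% power to detect an effect size of 0.4". The plan equates this effect with 4 percentage points on the exam score.
- A committed minimum, from an assumed average of 80 per cluster: 8 × 80 = 640 "residents at 8 university training sites".
- A conditional statement for the same effect size: "If residents at 12 sites are consented, we will have adequate power to detect an effect size of 0.4". No percentage is put on 'adequate', and no power is given for 8 sites.

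The paragraph ends by sending the reader elsewhere for the derivation: "We detail our calculation of the proposed sample size (and the design effect) in the appendix". The section on types of analysis sets a two-sided 0.05 level and bases the confirmatory conclusion on the confidence interval for the group effect.

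**The concern.** A flat promise of 80% power followed by an 'if' for the same effect looks like a retraction. With the effect size, cluster size, ICC and method all fixed, power of exactly 80% can hold at only one number of sites, and the paragraph does not say which.

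The number of clusters largely drives power in this design, and 640 residents at 8 sites is the only size to which the plan commits. If the 80% was worked out for 12 sites and only 8 took part, the chance of missing a true d = 0.4 would be about 37% (normal) or 43% (t) rather than 20%. A null result might then be judged against a power figure that belongs to a larger trial.

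**Working it through.** **Inputs from the plan.** d = 0.4; 80 residents per site; 8 or 12 sites; two-sided alpha 0.05.

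**Assumptions, not in the available text.** Sites split equally between arms (4 + 4 or 6 + 6); equal cluster sizes; no losses; no gain from covariate adjustment; ICC unknown and therefore varied.

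**Formulas.** With k sites per arm, design effect DE = 1 + 79 × ICC and SE(d) = √(2 × DE / (80k)). Normal power is Φ(0.4/SE − 1.96), the opposite tail being negligible. The small-sample version uses the noncentral t on 2k − 2 degrees of freedom.

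**The plan's own figure.** The 80% cannot be reproduced without the ICC, but one can ask which ICC would produce it. Under the normal approximation, 80% power needs 0.4/SE = 1.960 + 0.842 = 2.802, so SE = 0.1428 and SE² = 0.0204.

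- At 8 sites (320 per arm): DE = 0.0204 × 320 / 2 = 3.26, so ICC = 2.26/79 = 0.0286.
- At 12 sites (480 per arm): DE = 0.0204 × 480 / 2 = 4.89, so ICC = 3.89/79 = 0.0493.

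The t versions are ICC 0.0159 (DE 2.26) at 8 sites and 0.0376 (DE 3.97) at 12.

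**If the 80% belongs to 12 sites.** At 8 sites with DE = 4.89, SE = √(9.78/320) = 0.175 and 0.4/0.175 = 2.29. Power is Φ(2.29 − 1.96) = 63%, and the detectable d is 2.802 × 0.175 = 0.49. The t version gives 57%, with a detectable d of 0.53.

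**If the 80% belongs to 8 sites.** At 12 sites with DE = 3.26, SE = √(6.52/480) = 0.1166 and 0.4/0.1166 = 3.43. Power is Φ(3.43 − 1.96) = 93%. The t version gives 96%.

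**Range over assumed ICC (power, normal / t).**

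| ICC | DE | 8 sites | 12 sites |
|---|---|---|---|
| 0.01 | 1.79 | 97% / 88% | 99.6% / 99% |
| 0.02 | 2.58 | 88% / 75% | 97% / 93% |
| 0.03 | 3.37 | 79% / 64% | 92% / 86% |
| 0.04 | 4.16 | 70% / 55% | 86% / 78% |
| 0.05 | 4.95 | 62% / 48% | 80% / 71% |

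**Reading the results against the text.** For an ICC at or below 0.0286 (normal) or 0.0159 (t), both site counts give at least 80%, and the three statements agree. Above that, and up to 0.0493 or 0.0376, 12 sites reach 80% and 8 do not. The available text does not place the ICC in either band.

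**The case for a change.** The strongest case for a real fault has two parts.

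First, if 8 sites already gave 80%, the sentence about 12 sites would add little, so the natural inference is that 12 is the basis of the calculation.

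Second, the plan's own recruitment figures lead to 12. The opening says: "Each year, over 1,200 residents challenge the Family Medicine certification exam". The allocation section says "all Canadian universities will be stratified per the median number of residents by site", and the recruitment section says "each university will recruit at least 80% of their residents". Then 0.80 × 1,200 = 960 = 12 × 80, which would make 640 a floor at two thirds of expected enrolment (640/960 = 67%).

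Neither part settles it. Stating a sufficient condition does not say that anything smaller fails; the paragraph can equally be read as 80% at the minimum, with 12 sites as the more comfortable case. The 960 multiplies two lower bounds ('over' 1,200 and 'at least' 80%) and uses exam candidates in place of incoming residents. Even a correct forecast of enrolment would not show which site count the power was calculated for, since a trial may be powered on its minimum.

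What stands is narrower: the summary paragraph leaves the 80% without a site count and 'adequate' without a percentage. A reader has to go to the appendix to learn which is meant.

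**Conclusion.** No contradiction is shown, and no change to the plan follows. The product 8 × 80 = 640 is right, and the 80% can be neither confirmed nor refuted without the ICC. A shortfall to about 57–63% at 8 sites appears only if the 80% is assigned to 12 sites; the opposite assignment gives about 93–96% at 12 sites and no shortfall. The plan places the design effect in an appendix that was not available here, so its absence cannot be held against the plan.

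Naming the site count beside the 80% would make the paragraph clearer, but would alter nothing that is done. The allocation already covers all Canadian universities, so a lower power figure at 8 sites would not bring in further clusters. The mixed model and the two-sided 0.05 level stay the same. A null result will be judged on the reported 95% confidence interval, which shows the precision actually achieved whatever was projected. This is a gap that someone holding the appendix fills directly.

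The figures assume equal clusters of 80, equal numbers of sites per arm and no covariate adjustment. Unequal cluster sizes or losses would lower power, and the planned covariates could raise it. The conclusion does not depend on these, because it rests on the ICC being unknown here rather than on any one power value.

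### The confidence interval that decides the trial is not tied to the 6 to 10 between-site degrees of freedom that 8 to 12 universities provide

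*Combined protocol and SAP*

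**What the plan says.** All references are to the combined protocol and SAP.

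- **Type of analyses.** The primary analysis is a linear mixed model with study site as a random factor. Its fixed factors are "study group assignment (control / intervention), age, sex, completion of a graduate degree, and IMG status". The decision rule reads "Confirmatory assessment of the primary endpoint will be based on the confidence interval for the fixed effect estimate of" the randomised group term. The plan describes the resulting test as "implying a two-sided level of significance (against the null hypothesis of no effect) of 0.05". The section names no degrees-of-freedom method, reference distribution, permutation test, or choice between REML and ML. It commits in general terms to CONSORT for cluster trials and to unspecified recommendations for analysis.
- **Allocation.** Universities are the unit of randomisation, and "all Canadian universities will be stratified per the median number of residents by site". The order is then "Following randomization, recruitment will begin locally".
- **Sample size.** The plan claims 80% power for a standardised effect of 0.4, with 80 residents per cluster on average and a minimum of 8 sites (640 residents). It adds: "If residents at 12 sites are consented, we will have adequate power to detect an effect size of 0.4". For the inputs it says: "We detail our calculation of the proposed sample size (and the design effect) in the appendix". That appendix is not in the available text.

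**The concern.** An effect that varies only between clusters is estimated with a precision that must itself be learned from the spread of a few cluster means. With 8 to 12 sites that spread is poorly estimated, and a multiplier of 1.96 ignores this. An analyst could follow the plan to the letter, report a large-sample interval, and have a test whose true level is well above the stated 0.05. Another analyst, equally compliant, could use a t or Kenward-Roger interval and reach the opposite conclusion on the same data. That choice should not be open once scores are linked to group.

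The size stratum is a lesser matter. It was used to randomise but is not in the model, and whether it should be added depends on the reference distribution and on which sites take part.

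**Working it through.** **Inputs from the plan:** two-sided 0.05; effect d = 0.4; m = 80 residents per site; k = 8 or 12 sites; claimed power 80%. **Assumed:** 1:1 allocation; equal site sizes; intraclass correlation (ICC) of 0.016, 0.029 or 0.05 in the main simulations; size stratum explaining 0%, 10% or 30% of between-site variance.

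**1. The plan's own power.** The ICC is not in the available text, so 80% can be neither confirmed nor refuted. It can be solved backwards. With design effect DE = 1 + 79 × ICC, SE = √(4 × DE / (k × 80)).
- 8 sites, normal formula: ICC 0.0286, DE 3.26, SE = √(4 × 3.26 / 640) = 0.143, and 0.4 / 0.143 = 2.80, which gives 80%.
- 12 sites, normal formula: ICC 0.0493, DE 4.89, SE = √(4 × 4.89 / 960) = 0.143, again 80%.
- Noncentral t on k − 2 df: 80% is reached at ICC 0.016 (8 sites) or 0.038 (12).

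These give the first two ICCs used below; 0.05 is close to the 12-site normal value.

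**2. Type I error of a normal-based interval, site means.** If size is unrelated to score, the statistic follows t on k − 2 df, whatever the ICC. P(|t| > 1.96) is 9.8% on 6 df (8 sites) and 7.8% on 10 df (12 sites).

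**3. The same under REML,** with site variance bounded at zero and the model as written:

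| Sites | ICC 0.016 | ICC 0.029 | ICC 0.05 |
|---|---|---|---|
| 8 | 8.3% | 9.2% | 9.6% |
| 12 | 7.4% | 7.8% | 7.8% |

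Adding four resident-level covariates in a full mixed-model simulation (6,000-8,000 replicates) gave 7.7%, 10.1%, 9.8% and 7.4%, 7.7%, 8.5%. Over ICC 0.01 to 0.10, ML with 1.96 was worse: 9.8-14.0% (8 sites) and 8.8-10.3% (12).

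**4. If size is prognostic.** With a 30% share, balanced strata and the stratum omitted, the normal-based error falls to about 5-7% (8 sites) or 4-5% (12). The variance explained by the stratum stays in the standard error although balance has removed it from the comparison.

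**5. The t-based alternative.** Critical values are 2.447 (6 df) and 2.228 (10 df). 2.447 / 1.960 = 1.25 and 2.228 / 1.960 = 1.14. With REML and t on k − 2 df, type I error is roughly 3.6-5.0%; the low end is at 8 sites with ICC 0.016. At the ICCs where the normal formula gives 80% power, t-based power is 65% (8 sites) or 71% (12). In simulation at ICC 0.029 and 8 sites, the normal-based interval's rejection rate is 79%, against 65% for t.

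**6. The stratum, t-based, site means, balanced by arm.** At a 30% share, adding it moves power from 80% to 84%, 63% to 71% and 44% to 56% at 8 sites (the three ICCs in order). At 12 sites it moves from 97% to 98%, 88% to 93% and 71% to 81%. At a 10% share and 8 sites the change is −1 to +1 points. If size is irrelevant the cost is about 3 points (8 sites) or 1 (12). Added under a normal-based interval instead, it raises type I error to as much as 10.7% or 8.2%.

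**7. The stratum, t-based, site means, unbalanced.** Example: 8 sites split 1:3 and 3:1.
- Omission at a 30% share gives type I error of 6.3-6.7%; inclusion gives 5.0%.
- Inclusion costs 3-6 power points at that share (78% to 73%, 63% to 59%, 48% to 45%) and 12-15 points if size is irrelevant.
- With 12 sites split 2:4 and 4:2, omission gives 5.3%. Inclusion gains 1-7 points at a 30% share, but at ICC 0.05 takes power from 71% to 65% if size is irrelevant.

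**The case against.** The strongest reply is that this is an unspecified detail and not a wrong choice. A reader might infer that the trial will be tested at nearly 10%. The documents do not support that: they never say the interval is normal-based, and a t, Satterthwaite or Kenward-Roger interval would comply equally well. The 8-site figures also sit at the stated minimum, and all Canadian universities are to be randomised. This limits the claim to a conditional one. It does not remove it, because a standard large-sample interval complies with the plan yet misses the plan's own level. The CONSORT reference names no degrees-of-freedom method. The plan cites the missing appendix for sample size and design effect, not for inference in the primary model.

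A reader might also infer that leaving out the stratum is an error that inflates type I error, or that it must always be added. That is not supported either. Nothing in the documents shows that size predicts score. With a t-based interval and balanced strata, omission is at worst conservative. The unbalanced layouts are hypothetical, although randomising before local recruitment means that balance among participating sites is not assured. Even in the 8-site unbalanced example, inclusion loses power when size matters. The stratum is therefore secondary.

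It is also fair to say that the t-based remedy is itself slightly conservative at low ICC.

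**Conclusion.** The point holds as a gap in the confirmatory rule that should be closed. If a normal-based interval is used, the stated 0.05 becomes about 8-10% at 8 sites and 7-8% at 12 when size is unrelated to score, and about 4-7% at an assumed 30% share with the stratum omitted and balanced. These offsetting effects cannot be relied on to cancel, because the stratum's prognostic strength is unknown.

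The site-mean result in step 2 needs no ICC. The REML and power figures rest on assumed ICCs, the stratum figures on assumed shares, and all simulations on equal site sizes. That last assumption is a real limit for a stratum defined by size. For the stratum, neither the size nor the sign of its effect on power can be known from the documents.

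**What to change.** Before scores are linked to group:

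1. State that the primary model is fitted by REML and that the study-group interval uses a small-sample degrees-of-freedom method: Kenward-Roger, or t on sites minus the number of site-level parameters (sites minus 2 without the stratum, minus 3 with it).
2. With that in place, add the above/below-median size stratum as a fixed effect if participating sites are balanced by arm within stratum. If they are not, decide without reference to scores whether the stratum-adjusted model is primary or a sensitivity analysis, and record why. Do not add the stratum under a normal-based interval.
3. Report participating sites by arm and stratum, and restate power with the same degrees of freedom.

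The cost is wording only; no new data are needed, since site size is known from the randomisation. The statistical price is the wider interval and mild conservatism at low ICC shown in step 5, lower nominal power if the plan's 80% assumed the normal, and the stratum's costs in steps 6 and 7.

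### The averaged mean time to correct completion has no rule for uncompleted cases; as defined it conditions on completion, which the trial expects to differ by arm

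*Combined protocol and SAP*

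**What the plan says.** The section on primary and secondary outcome measures states that "our secondary outcome will be the number, percentage and time to completion of all correctly answered questions, per case". Time to completion is counted in days "from the study start date in 2017 to the date that test questions for that case were deemed to be correctly answered". A case that is never answered correctly has no such date.

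The section on the type of analyses then plans three things for this outcome:

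- a mean time to event for each resident, "calculated separately for each clinical case in the app, averaged and then compared across groups";
- a graphical summary: "These data will be described using a Kaplan-Meier curve";
- a model: "To account for clustering while adjusting for potential confounders, we will use a Cox regression model with a sandwich covariance structure". With it, "we will compare the hazard for this secondary outcome, between intervention and control groups, as of April 2019".

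An end of follow-up does exist. The section on allocation says "Participants will exit the study on the first day of their exam in the spring of 2019", and the eligibility section gives a delivery window of 70 weeks. The April 2019 date belongs to the Cox comparison. Neither date is tied to the averaged mean, and no sentence says how an uncompleted case enters it.

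**The concern.** If only completed cases have a time, the mean answers the question of how early the completed cases were completed. It ignores how many were never completed. The hypothesis behind this outcome is that "alerts to reinforcement of content result in greater resident engagement with test questions", so unequal completion is what the trial expects. Control residents receive no alerts, and in the intervention arm alerts to a case can be stopped on request after three attempts, so uncompleted cases are foreseeable in both arms. The two means would then rest on differently selected sets of cases, and randomisation would no longer protect the comparison.

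The outcome is intended to help explain a difference in exam scores. A completed-only mean could hide most of a real difference in time to completion, or disagree with the Kaplan-Meier curve and Cox model reported beside it. If the rule is left open, it could also be chosen after the data are seen.

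**Working it through.** **Inputs from the documents.** The app has 70 cases (section on trial interventions). The delivery window is 70 weeks, December 2017 to April 2019 (eligibility section). 70 × 7 = 490 days; counted from 1 December 2017 (day of month assumed), this ends on 5 April 2019, which agrees with the stated months.

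**Inputs not in the documents.** Completion shares and timing by arm are assumed throughout.

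**Definitions.** Let τ = 490, p the share of cases completed by τ, and m the mean day among completed cases; subscript 1 is intervention and 0 is control.

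- Completed-only mean = m.
- Restricted mean, counting uncompleted cases to τ = p·m + (1 − p)·τ.
- Gaps are control minus intervention, so a positive gap means earlier completion under intervention.
- Completed-only gap: C = m₀ − m₁.
- Restricted-mean gap: D = p₁(τ − m₁) − p₀(τ − m₀).
- Hence C − D = (1 − p₁)(τ − m₁) − (1 − p₀)(τ − m₀).

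The two gaps agree only if every case is completed or if these two terms happen to be equal.

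**Constant hazards.** With completed share F, λ = −ln(1 − F)/490, the completed-only mean is 1/λ − 490(1 − F)/F and the restricted mean is F/λ. For F = 0.6: 1/λ = 534.8, completed-only 534.8 − 326.7 = 208.1, restricted 0.6 × 534.8 = 320.9. In the table, gaps are computed before rounding.

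| Completed, intervention vs control | Completed-only means | Restricted means | C | D | C/D |
|---|---|---|---|---|---|
| 60% vs 30% | 208.1, 230.5 | 320.9, 412.1 | 22.4 | 91.3 | 25% |
| 80% vs 50% | 182.0, 216.9 | 243.6, 353.5 | 35.0 | 109.9 | 32% |
| 50% vs 40% | 216.9, 224.2 | 353.5, 383.7 | 7.3 | 30.2 | 24% |

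Under constant hazards the sign is never reversed; the difference is shrunk.

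**Other timing patterns.** Take 80% vs 50% completed and m₁ = 245.

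- D = 0.8 × 245 − 0.5(490 − m₀) is zero at m₀ = 490 − 196/0.5 = 98.
- C is zero at m₀ = 245.
- C = D when 0.5(490 − m₀) = 0.2 × 245 = 49, that is m₀ = 392.

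So the completed-only gap has the wrong sign for m₀ between 98 and 245, is too small between 245 and 392, and is too large above 392. The same three points are 0, 245 and 350 at 60% vs 30%, and 184, 245 and 286 at 50% vs 40%.

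**Worked examples at 80% vs 50%.** In the intervention arm one case is completed per week with every fifth missed: 56 of 70 completed, mean day 245, restricted mean (56 × 245 + 14 × 490)/70 = 294. In the control arm 35 of 70 are completed:

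| Control pattern | m₀ | Restricted mean | C | D |
|---|---|---|---|---|
| Weekly, weeks 1–35, then none | 126 | 308 | −119 | 14 |
| One every two weeks | 252 | 371 | 7 | 77 |
| Weekly, weeks 36–70 | 371 | 430.5 | 126 | 136.5 |
| Evenly over days 350–490 | 420 | 455 | 175 | 161 |

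Reversal, shrinkage and overstatement can therefore all occur, depending on usage that the documents do not describe.

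**The case against.** The strongest reply is that the plan never says uncompleted cases are dropped. It refers to a mean time to event with confidence intervals, describes the data with a Kaplan-Meier curve and models the same outcome with Cox regression; both methods ordinarily censor. A reader might infer that the plan excludes uncompleted cases, and the text does not support that: it is silent. A reader might also infer that the trial has no end of follow-up, but exam-day exit and April 2019 are both written down. What stands is narrower: neither date is attached to the mean. Even a mean read from the Kaplan-Meier curve needs a stated horizon when some cases are never completed.

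A second reply is that the Cox model carries the clustering and confounder adjustment, and that the planned percentage completed would expose unequal completion. Both are true, and both limit the damage. Neither corrects a separate mean comparison that is also to be reported.

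A third is that the reversal example is contrived. In it, unalerted controls complete a case every week for 35 weeks, against 28 cases in the alerted arm by day 245, and are level or ahead until day 301. The curves cross, and the restricted-mean gap is only 14 days. This is fair: reversal is possible, but nothing in the documents makes it likely. Shrinkage needs no such pattern.

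**Conclusion.** The point holds for the averaged mean only. As defined, that statistic conditions on completion. In the three constant-hazard pairs tabulated it shows 24–32% of the restricted-mean difference, and under other assumed patterns it can overstate or reverse it. The algebraic relation between the two gaps is exact; every size quoted rests on assumed completion shares and timing and on a 490-day horizon.

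Three stronger conclusions are not supported:

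- That the arm difference would be reversed: this depends on heavy early control use, which is an assumption.
- That the time-to-completion analysis as a whole is invalid: the Cox model and the percentage completed do not share the defect.
- That the trial's main result is at risk: confirmatory assessment rests on the exam score, and this outcome is secondary and explanatory.

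The plan should be changed because a better statistic is available at little cost from data already being recorded. This is not a defect that threatens the trial.

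**What to change.** - Replace the averaged mean with the restricted mean time to the exam date over all 70 cases per resident. Count uncompleted cases to that date, using a Kaplan-Meier-based estimate for residents who leave early. Compare it between arms with university as the cluster, adjusted for the same covariates.
- Name the planned Cox model, with uncompleted cases censored at the exam date, as the main comparison for this outcome. Report both beside the percentage completed in each arm.
- Report the restricted-mean difference whatever a proportional-hazards check shows, rather than switching to it on a diagnostic.

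A separate, minor point: the plan does not say at what level the Cox sandwich variance is clustered or whether it is corrected for few clusters. State that it is clustered on university, with a small-sample correction suited to 8 to 12 universities. With k universities per arm of equal size and a t reference on 2k − 2 degrees of freedom, intervals relative to an uncorrected sandwich widen by (t₀.₉₇₅/1.96) × √(k/(k − 1)). That is (2.447/1.96) × √(4/3) = 1.44 for 8 universities and (2.228/1.96) × √(6/5) = 1.25 for 12.

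The cost is a few sentences of analysis text, slightly more analysis work and, with the correction, wider intervals. The server already records the date and time of every attempt, so no new data are needed, and the primary analysis does not change.
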